### 3. OVERALL STUDY DESIGN AND PLAN

#### 3.1 Study Design

[figure not shown]
This is a phase 2a, multicenter, open-label, dose-escalation study to evaluate the safety and efficacy of DAXI for injection for the treatment of subjects with moderate to severe FHL in conjunction with GL treatment. This study will be conducted at 4 sites in the United States and Canada.

Subjects will be screened for eligibility and enrolled into the study after providing informed consent.

[figure not shown]
Approximately 60 subjects (18-65 years of age) with moderate to severe FHL will be enrolled

[figure not shown]
The total study duration will be up to 40 weeks including up to 2 weeks for screening. Subjects will be followed for a minimum of 24 weeks from GL treatment for safety or until all scores on the IGA-FWS and PFWS, as well as the IGA-FHWS and PFHWS return to baseline (Day 1 Visit prior to GL treatment) or until Week 38, whichever occurs first. Subjects will then have a Final Evaluation Visit. The intention is for subjects to be followed for a minimum of 24 weeks from FHL treatment (Week 26).

A Data Review Committee (DRC) will be used to review data from each cohort and will determine whether to proceed to the next cohort. If the DRC elects not to proceed with the FHL injection in a given dose cohort, subjects assigned to that cohort who have already received GL treatment will be followed for 14 weeks from the time of treatment (Day 1).

[figure not shown]

Statistical Analysis Plan for 1820202

### **3.1.1 Determination of Sample Size**

The sample size is not determined by the power of any hypothesis testing.

### **3.1.2 Treatments Administered**

This is an open-label, non-randomized study. Subjects will be sequentially enrolled by cohort. All subjects will receive DAXI for injection according to assigned cohort.

## **3.2 Efficacy and Safety Assessments**

The primary efficacy assessments will include investigator assessment of GL and FHL severity and improvement on the IGA-FWS and IGA-FHWS, respectively as well as subject assessment of severity and improvement of GL and FHL on the PFWS and PFHWS, respectively.

### **3.2.1 Frown and Forehead Wrinkle Severity**

Frown wrinkle severity is assessed by both the subject (PFWS) and the investigator (IGA-FWS) using the same 4-point rating scale, where scores range from 0 = none to 3 = severe.

Forehead wrinkle severity is assessed by both the subject (PFHWS) and the investigator (IGA-FHWS) using the same 4-point rating scale, where scores range from 0 = none to 3 = severe.

### **3.2.2 Patient Global Satisfaction with Treatment**

At each clinic visit after treatment, the subject will be asked to complete the Subject Global Satisfaction with Treatment Questionnaire to rate their satisfaction with the treatment results using a 7-point scale. The scale ranges from 0 = Very Dissatisfied to 6 = Very Satisfied, with a rating of 3 = Neither Satisfied nor Dissatisfied.

### **3.2.3 Global Aesthetic Improvement Scale**

The Investigator and subject will assess the visual appearance (at maximum eyebrow elevation) of the improvement from the baseline condition in FHL and in visual appearance in the improvement of GL during maximum frown using the 7-point severity GAIS. The scale ranges from -3 = Very much worse to 3 = Very much improved, with a rating of 0 = No change.

Statistical Analysis Plan for 1820202

### 3.2.5 Facial Age Self Evaluation

At each clinic visit, the subject will be asked to rate their perceived age using the FASE questionnaire (see Appendix 9 of the protocol).

### 3.2.6 FACE-QTM

At each clinic visit, the subject will be asked to complete the FACE-QTM Satisfaction with Forehead and Eyebrows and the FACE-QTM Appraisal of Lines: Forehead questionnaires (see Appendix 11 of the protocol). The questionnaires ask subjects to rate how bothered they are by their FHL using 6 questions about general appearance with a rating scale of 1 to 4 with 1 = Not Bothered and 4 = Extremely Bothered. The final question related to the number of forehead lines was not included in the study assessment.

[REDACTED]

## 3.3 Safety Assessments

### 3.3.1 Adverse Events

All adverse events (AEs) will be recorded and classified on the basis of MedDRA terminology. AE severity will be graded as mild, moderate, or severe as defined in Section 9.3.2 of the protocol. Relationship of an AE will be graded as definite, probable, possible, or unrelated. AEs with an onset on or after the date and time of trial treatment or events which were present before treatment and which worsened after treatment will be considered as treatment-emergent.

AEs with missing severity will be considered as “severe”. AEs with missing relationship will be considered as “related”. If the start of an AE relative to the administration of trial treatment cannot be definitively determined, it will be considered to have occurred after treatment and the event considered as treatment-emergent.

[REDACTED]

### 3.3.3 Injection Site Evaluation

Injection sites will be evaluated at screening for signs of skin inflammation or active disease. The GL treatment areas will be evaluated at Day 1 (pre- and post-treatment) and at Weeks 2 and 4. The FHL treatment areas will be evaluated at Week 2 (pre- and post-treatment) and at Weeks 4 and 6. The

## Statistical Analysis Plan for 1820202

assessment will be done as a global evaluation of the 5 injection sites for GL and 3 injection sites for FHL. The presence of erythema, edema, burning or stinging, itching or bruising will be captured as medical history (pre-treatment) or as an AE (post-treatment).

### 3.3.4 Clinical Laboratory Data

As outlined in [Table 3.3.4-1](#), non-fasting samples for hematology, chemistry, PT (screening only) and urinalysis will be collected at screening, the Week 4 Visit, and the Week 38 or Final Evaluation Visit. [REDACTED] Urinalysis will be evaluated at the study center.

Urine pregnancy tests (UPT) will be performed at screening, prior to treatment administration at Baseline and Week 2, and at the Week 38 or Final Evaluation Visit. A serum pregnancy test will be performed to confirm pregnancy whenever a post-treatment UPT is positive.

**Table 3.3.4-1: Clinical Laboratory Tests**

Serum Chemistry	Hematology	Urinalysis	Additional Tests
Glucose	Hemoglobin	Specific gravity	Prothrombin time (PT) (screening only)
Total bilirubin	Hematocrit	pH	
Alanine aminotransferase	Leukocyte Count (total)	Glucose	UPT (WOCBP only)*
		Protein	
Aspartate aminotransferase	Leukocyte Count (differential)	Blood	[REDACTED]
		Bilirubin	[REDACTED]
Alkaline phosphatase	Red Blood Cell Count	Ketones	
Blood urea nitrogen	Platelet Count		

WOCBP = Women of child-bearing potential

### **3.3.6 Vital Signs**

Vital signs (i.e., body temperature, respiration rate, sitting radial pulse rate, and sitting systolic and diastolic blood pressures) will be obtained at the screening, Day 1, Week 2, and Week 38 or Final Evaluation Visits, [REDACTED]

New abnormal findings or worsening from baseline (Day 1 prior to GL treatment) at subsequent assessments, if judged clinically significant, should be recorded as an AE.

### **3.3.7 Physical Examination**

A targeted physical examination, [REDACTED], will be conducted at screening, Day 1, Week 2 and Final Evaluation Visits. Significant physical examination findings that are present prior to investigational product administration will be reported as Medical History.

Significant physical examination findings after investigational product administration which meet the definition of an AE will be recorded as an AE.

## **3.4 Interim Analyses and Data Monitoring**

### **3.4.1 Data Review Committee**

Due to the dose-escalation nature of the study design, safety data and subject photographs/videos will be evaluated by the DRC at Week 5 following GL treatment (3 weeks after FHL treatment) for each cohort before a decision is made to move forward with the next and subsequent doses. If the DRC elects not to

## Statistical Analysis Plan for 1820202

proceed with the FHL injection in a given dose cohort, subjects will be followed for 14 weeks from the time of treatment (Day 1).

Dose escalation for FHL may be stopped at the discretion of the DRC as outlined in the DRC Charter. The full details for the roles and responsibilities of the DRC will be detailed in the study-specific DRC charter.

### **3.4.2 Interim Analysis**

A formal interim analysis of the data will be performed when all subjects finish 8 weeks after receiving the FHL treatment or have withdrawn from the study earlier. This interim analysis will be a high level analysis of study conduct, efficacy and safety. The analysis will be performed by the study team in a restricted access folder. Efficacy will focus on the primary and secondary endpoints.

Individual tables, listings, and figures to be included in the interim analyses are denoted in [Section 9](#) below with an asterisk.

## **4. ANALYSIS POPULATIONS AND SUMMARY GROUPS**

Five analysis populations will be specified, ignoring cohort membership. These populations are: Enrolled, GL-Evaluable, FHL-Evaluable, Safety and Safety-FHL. Analyses performed on the Enrolled, GL-Evaluable and FHL-Evaluable population will utilize the planned treatment assignment(s). Analyses performed on the Safety and Safety-FHL populations will utilize the actual treatment(s) received.

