## 4. Study Design

### 4.1. Overall Design

[figure not shown]
This is a phase 2a, multicenter, open-label, dose-escalation study to evaluate the safety and efficacy of DAXI for injection for the treatment of subjects with moderate to severe FHL in conjunction with GL treatment. This study will be conducted at 4 sites in the United States and Canada.

Subjects will be screened for eligibility and enrolled into the study after providing informed consent.

Approximately 60 subjects (18-65 years of age) with moderate to severe FHL will be enrolled and sequentially assigned to 1 of 4 treatment cohorts (15 subjects per cohort) to receive DAXI for injection. Investigators will make all reasonable efforts to enroll equal proportions of patients with moderate and severe FHL (based on baseline assessments) in each dosing cohort.

The total study duration will be up to 40 weeks including up to 2 weeks for screening. Subjects will be followed for a minimum of 24 weeks from GL treatment for safety or until all scores on the IGA-FWS and PFWS, as well as the IGA-FHWS and PFHWS return to baseline (Day 1 Visit prior to GL treatment) or until Week 38, whichever occurs first. Subjects will then have a Final Evaluation Visit. If the DRC elects not to proceed with the FHL injection in a given dose cohort, subjects assigned to that cohort who have already received GL treatment will be followed for 14 weeks from the time of treatment (Day 1).

Sequential enrollment will occur for each cohort. The first cohort will be enrolled and treated. The DRC will convene to review available data (including safety, efficacy, and photographs/video) at Week 5 following GL treatment (3 weeks after FHL treatment) for each cohort before a decision is made to move forward with the next and subsequent doses. Revance reserves the right to terminate or stop the study at any time. Refer to Sections 1.2 and 9.4.1 for additional information.

All subjects will be evaluated for FHL severity using the Revance-validated 4-point IGA-FHWS and PFHWS at rest and at maximum eyebrow elevation, as assessed by both the investigator and the subject. In addition, to determine the efficacy response to the glabellar complex, subjects will be evaluated for improvement on the IGA-FWS and the PFWS at rest and at maximum frown.

[figure not shown]

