### 9.2. Populations for Analyses

For purposes of analysis, the following populations are defined and the summary groups for analysis will be based on the actual dose for FHL received (which is expected to be consistent with the enrollment cohorts):

Population	Description
Enrolled	All subjects who receive the GL treatment
GL-Evaluable	All enrolled subjects who have any post-GL treatment assessment of IGA-FWS at maximum frown
FHL-Evaluable	All enrolled subjects who receive the FHL treatment and have any post-FHL treatment assessment of IGA-FHWS at maximum eyebrow elevation
Safety	All enrolled subjects
Safety-FHL	All enrolled subjects who receive the FHL treatment

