## 6.5 Efficacy Analyses

Descriptive statistics will be provided for all efficacy variables at all visits by cohort. A 95% exact CI will be provided for proportions. All analyses displaying proportions will use population counts as denominators at all visits regardless of the number of actual observations recorded. Differences between cohorts will not be presented except where specifically identified in the shells.

The Efficacy GL population will be used when analyzing endpoints associated with GL.

[figure not shown]
The Efficacy FHL population will be used when analyzing endpoints associated with FHL.

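### SAP Section 4 groups FHL efficacy by planned cohort, whereas protocol 9.2 groups by the FHL dose actually received; safety uses actual treatment, and SAP Section 6.7 does not list the departure

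*SAP*

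**What the plan says.** Protocol Section 9.2 sets one grouping rule ahead of its table of five populations: "summary groups for analysis will be based on the actual dose for FHL received (which is expected to be consistent with the enrollment cohorts".

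SAP Section 4 splits that rule in two:

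- Efficacy and enrolment: "Analyses performed on the Enrolled, GL-Evaluable and FHL-Evaluable population will utilize the planned treatment assignment(s".
- Safety: "Analyses performed on the Safety and Safety-FHL populations will utilize the actual treatment(s) received".

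For forehead-line endpoints, SAP Section 6.5 says "The Efficacy FHL population will be used when analyzing endpoints associated with FHL". No population of that exact name is defined; I take it to be FHL-Evaluable, which puts the primary endpoint under the planned-assignment rule. SAP Section 6.5.1 applies a stratified Cochran-Mantel-Haenszel test and an exact Cochran-Armitage trend test to that endpoint.

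On allocation, SAP Section 3.1.2 says "This is an open-label, non-randomized study. Subjects will be sequentially enrolled by cohort". SAP Section 6.7 reports one change from the planned analyses, the replacement of the stratified exact logistic regression. It does not mention the grouping rule.

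**The concern.** Two current documents give different rules for which dose group a subject belongs to in the primary analysis, and nothing in the visible text explains why. The usual reason for analysing as assigned is to keep a randomised comparison intact. There is none here: dose is set by the cohort open at the time of enrolment. In a study that asks how response changes with FHL dose, counting a subject at a dose not received is simply exposure misclassification.

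The primary objective covers efficacy and safety together. Under the SAP, the same subject could contribute a response to one dose and adverse events to another, so the two sets of tables would not be like for like at each dose. Leaving both rules in place also allows the choice between them to be made after the data are seen.

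**Working it through.** **Inputs.** Four cohorts of 15: "sequentially assigned to 1 of 4 treatment cohorts (15 subjects per cohort) to receive DAXI for injection" (protocol Section 4.1). Total 4 × 15 = 60, which agrees with the approximate 60 stated. There is no power figure to reproduce: "The sample size is not determined by the power of any hypothesis testing" (SAP Section 3.1.1). The documents give no rate of misdosing and no expected response rates, so anything that needs them below is an assumption.

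**Who is affected.** FHL-Evaluable contains only subjects who received FHL treatment. Those who had GL treatment alone are therefore outside the primary analysis. For that analysis, the two rules differ only for a subject given an FHL dose other than the planned one.

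**Effect on a cohort's response rate.** Let x of 15 respond under planned grouping, and regroup one subject by actual dose.

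- A non-responder leaves: x/14 − x/15 = x/210.
- A responder leaves: x/15 − (x−1)/14 = (15−x)/210.
- A non-responder joins: x/15 − x/16 = x/240.
- A responder joins: (x+1)/16 − x/15 = (15−x)/240.

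The largest shift for a cohort that loses a subject is 14/210 = 6.7 points. It occurs when 14/15 loses its only non-responder or 1/15 loses its only responder. The largest for a cohort that gains one is 15/240 = 6.3 points.

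From 12/15 = 80.0% (exact 95% CI 51.9 to 95.7):

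| Change | Result | Shift (points) | 95% CI |
|---|---|---|---|
| Responder leaves | 11/14 = 78.6% | 1.4 down | 49.2 to 95.3 |
| Non-responder leaves | 12/14 = 85.7% | 5.7 up | 57.2 to 98.2 |
| Non-responder joins | 12/16 = 75.0% | 5.0 down | 47.6 to 92.7 |

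**Effect on the trend test.** Assume planned responders of 8, 10, 11 and 13 out of 15, with dose scores 1 to 4. The p-value is the exact two-sided conditional Cochran-Armitage probability: the share of all tables with the same margins whose score total lies at least as far from its expectation as the observed one.

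| Grouping | Responders / n by dose | p |
|---|---|---|
| Planned | 8/15, 10/15, 11/15, 13/15 | 0.060 |
| Actual: a cohort 4 non-responder received the cohort 3 dose | 8/15, 10/15, 11/16, 13/14 | 0.030 |
| Actual: a cohort 3 responder received the cohort 4 dose | 8/15, 10/15, 10/14, 14/16 | 0.048 |
| Actual: a cohort 1 non-responder received the cohort 4 dose | 8/14, 10/15, 11/15, 13/16 | 0.169 |

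One subject can strengthen or weaken the apparent trend, depending on who was misdosed and in which direction.

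**Chance that the question arises.** With an assumed misdosing probability p per subject, the chance of at least one case among 60 is 1 − (1−p)^60. This gives 45% at 1%, 70% at 2% and 95% at 5%. These rates are illustrative only.

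**The case against.** The strongest reply is that the difference may never matter. The protocol expects actual dose to match the cohort. Cohorts open one at a time after DRC review, FHL dosing needs DRC approval of the intended dose, and a trained preparer makes up the syringe. A cohort 1 subject receiving the cohort 4 dose, as in the last table row, is unlikely under that design. Misdosing would also be visible, because SAP Section 6.6.1 summarises the dose injected and SAP Section 6.1 lists major deviations. The analyses are exploratory, and the interval at 12/15 is already wide. All of this stands and limits the size of the point. It does not reconcile the two rules, and seeing a misdosed subject in a listing does not move that subject in the primary table.

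A second reply is that planned cohort is needed somewhere. Protocol Section 6.5 allows a subject to receive GL treatment and no FHL treatment. Such a subject has no actual FHL dose, yet belongs to the Enrolled population and, if assessed, to GL-Evaluable. This also stands: for those tables the SAP rule fills a gap in protocol 9.2. A reader might infer that planned grouping should survive only for disposition; that would leave these subjects without a group.

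A reader might also infer that misclassification must flatten the dose-response. That tends to hold on average when response rises with dose, but with one or two subjects the shift can go either way, as the table shows. Nor would a common grouping rule make efficacy and safety tables hold identical subjects: FHL-Evaluable requires an IGA-FHWS assessment after FHL treatment and Safety-FHL does not, which is an intended difference.

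Finally, the text after SAP Section 4.5 is largely blacked out, so a further handling rule there cannot be excluded. It would have to qualify an explicit sentence in Section 4.

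**Conclusion.** The inconsistency is real and should be corrected. Protocol 9.2 groups by actual FHL dose; SAP Section 4 groups FHL-Evaluable analyses, including the primary endpoint and the dose-response tests, by planned assignment, and Section 6.7 does not record the departure. Planned grouping has no design justification for these analyses.

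The size is modest and conditional. It is zero if planned and actual FHL doses agree for every treated subject. Otherwise each discrepant subject moves a cohort's rate by at most 6.7 percentage points, usually less, and can carry the exploratory trend test across 0.05 in either direction under the assumed counts. The 6.7 points is a ceiling reached only at 14/15 or 1/15, not a typical value. The documents do not show that any subject was misdosed, so they do not support reading the primary result as already biased. Protocol Section 9.3 plans no formal hypothesis tests, so what is at stake is the reading of dose-response and of benefit against risk at each dose, not type I error.

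This rests on cohorts of 15, on reading the Efficacy FHL population as FHL-Evaluable, and on no contrary rule in the redacted text.

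**What to change.** In SAP Section 4, state that FHL-Evaluable analyses, including the primary endpoint and the dose-response tests, are grouped by the FHL dose actually received, in line with protocol 9.2 and with Safety-FHL. Keep planned cohort for the Enrolled and GL-Evaluable tables, where subjects without FHL treatment have no actual FHL dose. List that remaining departure from protocol 9.2 in SAP Section 6.7, with this reason. If the redacted text does not already say how a partial FHL dose is classified for analysis, the same edit should say so, since SAP Section 4.1 counts partially dosed subjects as enrolled.

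The cost is a short edit to Section 4 and an entry in Section 6.7. No new data are needed: actual treatment is already required for Safety-FHL, and the dose injected is already summarised under SAP Section 6.6.1. Sample size is unaffected.

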### **4.1 Enrolled Population**

All subjects who receive the GL treatment. A subject will be considered “enrolled” if they receive any investigational product including a partial dose.

### **4.2 GL-Evaluable Population**

All enrolled subjects who have any post-GL treatment assessment of IGA-FWS at maximum frown.

### **4.3 FHL-Evaluable Population**

All enrolled subjects who receive the FHL treatment and have any post-FHL treatment assessment of IGA-FHWS at maximum eyebrow elevation.

### **4.4 Safety Population**

All enrolled subjects.

### **4.5 Safety-FHL**

All enrolled subjects who receive the FHL treatment.

[REDACTED]

[REDACTED]

[REDACTED]

[REDACTED]

[REDACTED]

Statistical Analysis Plan for 1820202

Cohort 4: DAXI 30 U

## 5. CONVENTIONS AND DERIVATIONS

### 5.1 Definition of Baseline

The baseline value will be the last available non-missing value prior to GL treatment on Day 1. Assessments taken on the same day as GL treatment will be assumed to be prior to treatment unless indicated to be obtained post-treatment.

### 5.2 Definition of Day 1

#### 5.2.1 GL Treatment

Study Day 1 is defined as the day of the DAXI 40 U dose for GL treatment. All time-to-event analyses for assessments of GL will utilize the date of study day 1 as the start date.

#### 5.2.2 FHL Treatment

Day 1 of FHL treatment is defined as the day of DAXI dose for FHL treatment. All time-to-event analyses for assessments of FHL will utilize the date of FHL treatment as the start date.

Note that this definition allows for delays in administration of DAXI for FHL treatment and requires a relative day variable to be derived for days post-FHL treatment.

### 5.3 Demographic and Disposition

Age in years at time of enrollment will be derived relative to the date of informed consent as (consent date – date of birth + 1)/365.25 and truncated to 0 decimal points. Age will also be categorized into two groups: <65 years and  $\geq$ 65 years.

